4.3.2. Subject Exclusion Criteria

Subjects eligible to participate in this study must not meet any of the following exclusion criteria:

1. Women who are pregnant, planning to become pregnant or lactating*.

** Includes breastfeeding or planning to breastfeed at any given time from the receipt of study vaccination through the 6-month trial period.*

2. Known allergy or history of anaphylaxis, severe local or other serious adverse reactions to vaccines or vaccine products%, or history of severe allergic reactions.

% Includes a known allergy to egg, egg products and aminoglycosides or any of the constituents of the study vaccines [e.g., polysorbate 80, ethylenediaminetetraacetic acid (EDTA), L-histidine, tris (hydroxymethyl)-amino methane (THAM)].

3. Received an experimental agent⁵ within 3 months prior to Day 1, or expects to receive an experimental agent⁶ during the 6-month trial-reporting period.

⁵ Including vaccine, drug, biologic, device, blood product, or medication.

⁶ Other than from participation in this study.

4. Received immunoglobulin or other blood product within 3 months before enrollment in this study.

5. Received any licensed live vaccine within 30 days prior to the first study vaccination through 30 days after the second study vaccination.

6. Received a licensed inactivated vaccine within 14 days prior to the first study vaccination through 14 days after the second study vaccination.

7. Has been vaccinated with an Ebola vaccine.

8. Has been diagnosed with Ebola disease, or exposed to Ebola virus including travel to West Africa[^] in 2014-2016.

[^] West Africa includes but is not limited to the countries of Guinea, Liberia, Mali, Nigeria, and Sierra Leone.

9. Known or suspected receipt of ChAd3-EBO-Z or other ChAd3-vectored vaccine.

10. Known or suspected receipt of an adenovirus serotype 5 (Ad5)-based vaccine.

11. Known or suspected receipt of any licensed or investigational small pox (vaccinia)-based vaccine[#].

[#] Includes any MVA-based candidate vaccine (Imvamune or Imvanex), Dryvax, or Acam2000.

12. Has a typical vaccinia scar.

13. Confirmed Asplenia/Functional Asplenia.

14. A history of bleeding or clotting disorders.

15. Thyroidectomy or thyroid disease requiring medication during the last 12 months.

16. History of chronic urticaria (recurrent hives).

17. Individuals in whom the ability to observe possible local reactions at the eligible injection sites (left and right deltoid region) is, unacceptably obscured due to a physical condition or permanent body art.

18. Have an acute illness[#], as determined by the site PI or appropriate sub-investigator, within 72 hours prior to study vaccination.

[#] An acute illness which is nearly resolved with only minor residual symptoms remaining is allowable if, in the opinion of the site PI or appropriate sub-investigator, the residual symptoms will not interfere with the ability to assess safety parameters as required by the protocol. Subjects may re-screen after an acute illness is resolved.

19. Any confirmed or suspected immunosuppressive or immunodeficient condition* or use of anticancer chemotherapy or radiation therapy (cytotoxic) within 3 years prior to study vaccination
 - * including HIV infection.
20. Administration of chronic (defined as more than 14 days) immunosuppressants or other immune modifying drugs within 6 months of receipt of study vaccine.
21. Have taken oral or parenteral (including intraarticular) corticosteroids of any dose within 30 days prior to study vaccination.
22. Have taken high-dose³ dose inhaled corticosteroids within 30 days prior to study vaccination.
 - ³ High-dose defined using the inhaled high-dose reference chart (Appendix B in the protocol).
23. Have a history of convulsions or encephalomyelitis within 90 days prior to study vaccination.
24. Current or past history of alcohol or drug abuse in the last 5 years.
25. Subjects with autoimmune disorders, chronic inflammatory disorders or neurological disorders with a potential autoimmune correlation.
26. Have any diagnosis, current or past, of schizophrenia, bipolar disease, or other psychiatric diagnosis that may interfere with subject compliance or safety evaluations.
27. Have been hospitalized for psychiatric illness, history of suicide attempt, or confinement for danger to self or others within 10 years prior to study vaccination.
28. Have received any antiviral within 3 days of study vaccination
29. History of myocarditis, pericarditis, cardiomyopathy, transient ischemic attack or stroke, myocardial infarction, angina, coronary artery disease, congestive heart failure, clinically significant arrhythmia*
 - * including any arrhythmia requiring medication, treatment, or clinical follow-up.
30. Electrocardiogram (ECG) with clinically significant findings.*
 - * Clinically significant findings include the following:
 - a. Conduction disturbance (complete left or complete right bundle branch block or nonspecific intraventricular conduction disturbance with QRS \geq 120 ms, PR interval \geq 210 ms, any second- or third-degree atrioventricular block, or prolongation of the QT interval corrected according to Bazett's formula [QTcB] [$>$ 450 ms]).
 - b. Significant repolarization (ST-segment or T-wave) abnormality.
 - c. Significant atrial or ventricular arrhythmia; frequent atrial or ventricular ectopy (e.g., frequent premature atrial contractions, 2 premature ventricular contractions in a row).
 - d. ST-elevation consistent with ischemia or evidence of past or evolving myocardial infarction
31. A diagnosis of Type I or II diabetes. (A history of isolated gestational diabetes is not an exclusion criterion).
32. Current employee or staff paid entirely or partially by the contract for this trial, or staff who are supervised by the PI or Sub-Investigators.

33. Any condition that would, in the opinion of the Site Investigator or appropriate sub-investigator, is a contraindication to study participation.*

* *Including acute or chronic (persisting for at least 90 days) clinically significant medical disease or condition, that would place the subject at an unacceptable risk of injury, render the subject unable to meet the requirements of the protocol, or may interfere with the evaluation of responses or the subject's successful completion of the study.*

4.4. Treatments

4.4.1. Treatments Administered

Zaire ebolavirus (ChAd3-EBO-Z) vaccine, consisting of a recombinant, replication-defective chimpanzee adenovirus (Ad) type 3 (ChAd3)-derived vector expressing the *Zaire ebolavirus* glycoprotein (GP) was administered by intramuscular (IM) injection into the deltoid muscle in a single dose of 2×10^{11} vp virus particles.

MVA-BN®-Filo 1×10^8 Infectious Units (IU) of replication defective MVA-BN®-Filo was administered in the form of an injection into the deltoid muscle (heterologous boost together with 2×10^{11} vp ChAd3-EBO-Z).

Sodium Chloride Injection USP, 0.9% (NaCl 0.9%, Normal Saline) was used as the placebo booster injection into the deltoid muscle.

4.4.2. Identity of Investigational Product(s)

See the study manual of procedures for details of study product formulation. Additional details are included in the investigator's brochure for each investigational product.

4.4.3. Method of Assigning Subjects to Treatment Groups (Randomization)

Once consented and upon entry of demographic data and confirmation of eligibility for this trial, the subjects were enrolled. Subjects were randomized 1:1:1 in double-blind fashion to 1 dose of ChAd3-EBO-Z vaccine at Day 1 followed by a booster of placebo, ChAd3-EBO-Z (homologous), or MVA-BN®-Filo (heterologous) at Day 8.

Enrollment of subjects was done online using the enrollment module of AdvantageEDCSM. The randomization code was prepared by statisticians at the SDCC and included in the enrollment module for this trial. AdvantageEDCSM was used to assign each subject to a treatment arm after the demographic and eligibility data had been entered into the system.

Subjects who signed the informed consent form and were randomized but did not receive study vaccine may have been replaced. Subjects who signed the informed consent form, and were randomized and vaccinated, and subsequently withdrew, or were withdrawn or terminated from this trial, or were lost to follow-up might have been replaced.

4.4.4. Selection of Doses in the Study

The dosing was recommended by the manufacturers based on results from multiple previous clinical trials.

4.4.5. Selection and Timing of Dose for Each Subject

The rationale for the short prime-boost (timing between Dose 1 and 2) schedule was to assess suitability to provide protective immunity rapidly in an outbreak setting. In addition, it minimizes the risk of post-immunization anti-vector (ChAd3) antibodies interfering with the boost response.

4.4.6. **Blinding**

This was a double-blind clinical trial. Subjects, investigators, study personnel performing any study-related assessments following study vaccine administration, and laboratory personnel performing antibody assays were blinded to treatment arm assignment (i.e., type of booster). Laboratory personnel performing experimental assays including antibody assays were also masked to subject ID and study visit. The randomization scheme was generated by the SDCC and provided to unblinded study personnel (i.e., research pharmacists performing study vaccination preparations and unblinded study vaccine administrators) at the participating VTEU site.

To preserve blinding and mask the color of study product in the syringe, the unblinded site research pharmacist was to place a blinding tape or overlay on the syringe to mask its content. The vaccine was then be sent to an unblinded study vaccine administrator for administration to the subject.

The unblinded study vaccine administrator was a study personnel member credentialed to administer vaccines and might also have participated in dose preparation, but was not involved in study-related assessments or had subject contact for data collection following study vaccine administration.

The Safety Monitoring Committee (SMC) received data in aggregated form across study arms. The SMC was to review safety data by study arm in the closed session only. Refer to the protocol-specific Manual of Procedures (MOP) for unblinding procedures.

4.4.7. **Prior and Concomitant Therapy**

Administration of any medications, therapies, or vaccines were recorded on the appropriate data collection form. Concomitant medications included all current medications and medications taken within 60 days prior to signing the informed consent form through approximately 28 days after the second study vaccination or early termination (if prior to 28 days after the second study vaccination), whichever occurred first.

Assessment of study eligibility included a review of all permitted and prohibited medications per the Subject Inclusion and Exclusion Criteria (see Section 4.3). Medications reported in the electronic case report form (eCRF) were limited to those taken within 30 days prior to study vaccination through approximately 28 days after the second study vaccination. Prescription and over-the-counter drugs were included as well as herbals, vitamins, and supplements. In addition, receipt of non-study vaccines was solicited through approximately 28 days after the second study vaccination and reported in the eCRF.

Use of new medication prompted evaluation for the occurrence of an AE or worsening of a pre-existing medical condition. Medications that might interfere with the evaluation of the investigational product(s) were not to be used from time of study vaccination through 28 days post the second vaccination unless clinically indicated as part of the subject's health care. Medications in this category included the prohibited medications per the Subject Exclusion Criteria (see Section 4.3). In addition, the site principal investigator or appropriate sub-investigator may have identified other medications that should have not been used due to a risk to subject safety or assessment of reactogenicity and immunogenicity. Use of medications as prophylaxis prior to study vaccination was prohibited. There are no known drug-vaccine interactions with the study vaccine and subjects were not being asked to discontinue current medications not listed in the exclusion criteria. In the event medical conditions dictated use of medications, subjects were encouraged to obtain adequate care, comply with the course of therapy as prescribed by their physician and inform the site as soon as practicable. Details of all medications taken during the medication reporting period for this study (date, indication, brand or generic name) were recorded.

4.4.8. Treatment Compliance

Study products were administered to subjects via intramuscular injection by study personnel according to randomized subject treatment assignment. No dose modifications were planned. If a subject's second vaccination was deferred, attempts were made to reschedule the vaccination to occur within the acceptable protocol-specified window for that visit.

4.5. Immunogenicity and Safety Variables

See [Table 2](#) and Section 8 in the protocol for details on study procedures/evaluations.

4.5.1. Safety Variables

Safety will be assessed by the occurrence of:

1. Serious adverse events and MAAEs occurring from the time of study vaccination through approximately 6 months after the first study vaccination.
2. Solicited Adverse Events – reactogenicity events occurring from the time of study vaccination through 7 days after each study vaccination:
 - a) Local AEs including pain, tenderness, erythema (redness), induration (hardness/swelling), ecchymosis (bruising) and pruritis (itching).
 - b) Systemic AEs including fever, feverishness (chills, shivering, sweating), fatigue (tiredness), malaise (general unwell feeling), myalgia (body aches/muscular pain), nausea, loss of appetite and headache.
3. Clinical safety laboratory adverse events occurring from the time of study vaccination through approximately 28 days after the second vaccination. Parameters to be evaluated include WBC, Hgb, platelet count, ANC, sodium, potassium, Creatinine, BUN (BUN will be obtained only if creatinine is above the normal range), and ALT.
4. Unsolicited Adverse Events – study vaccine-related non-serious adverse events occurring from the time of study vaccination through approximately 28 days after the second study vaccination.

4.5.2. Immunogenicity Variables

The secondary immunogenicity endpoints will assess antibodies against Ebola virus (EBOV) glycoproteins (GP) using an enzyme-linked immunosorbent assay (anti-EBOV GP ELISA). Venous blood samples for serum used for this immunogenicity assay will be tested at pre-vaccination (Day 1) and post-vaccination on Days 8, 15, 22, 29, and 36 for all study arms. Analysis variables include geometric mean titer (GMTs), geometric mean fold rise (GMFR), and seroconversion.

The exploratory immunogenicity endpoints assess neutralizing antibodies using an anti-EBOV GP pseudovirion neutralization assay (anti-EBOV GP NEUT) at pre-vaccination (Day 1) and post-vaccination on Days 8, 15, 22, 29, and 36 for all study arms. The anti-EBOV GP NEUT endpoint will be represented as the highest titer achieving $\geq 50\%$ neutralization (anti-EBOV GP NEUT50) as well as the highest titer achieving $\geq 40\%$ neutralization (anti-EBOV GP NEUT40). Summary statistics for these anti-EBOV GP NEUT endpoints include geometric mean titer (GMTs) and geometric mean fold rise (GMFR).

4.5.3. Other Variables

Please refer to the addendum of this SAP for additional exploratory endpoint variables.

5. SAMPLE SIZE CONSIDERATIONS

This Phase I study is not designed to test a formal null hypothesis. The sample size for this study was selected to obtain preliminary estimates of vaccine safety and immunogenicity. The clinical trial includes an exploratory systems biology component to identify changes in gene expression, and cytokines that are associated with adaptive humoral and/or cellular immune responses. These systems biology results are expected to generate hypotheses to be verified in future studies.

6. GENERAL STATISTICAL CONSIDERATIONS

6.1. General Principles

Continuous variables will be summarized using descriptive statistics: n (non-missing sample size), mean, standard deviation, median, interquartile range, min, and max) unless otherwise specified. The frequency and percentages (based on the analysis population size) of observed levels will be reported for all categorical measures. In general, all data will be listed, sorted by study arm (1-3), subject, and when appropriate, by study visit number within subject. Unless otherwise specified, study arm labels shown in tables and figures will include the total population size relevant to the particular analysis. As subjects in all study arms will receive the same study product (ChAd3-EBO-Z) for the first vaccination (Table 1), results prior to the second vaccination (up to and including Day 8) will be presented jointly as “Study Arms 1, 2, and 3 (ChAd3)”. Post-second vaccination results will be presented separately for each of the three study arms.

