11.4.5. Missing Values and Outliers

All attempts will be made to collect all data per protocol.

As missing data are expected to be minimal, no imputation will be performed for missing values. Any data point that appears to be erroneous or inexplicable based on clinical judgment will be investigated as a possible outlier. If data points are identified as outliers, sensitivity analyses will be performed to examine the impact of including or excluding the outliers. Any substantive differences in these analyses will be reported.

For the transcriptomics endpoint, extreme data points will be identified by inspecting global patterns in the data. Experimental meta-data will be examined to see whether the outlying pattern can be attributed to experimental error such as sample mislabeling. Excluded outliers will be documented in the CSR. Due to the complexity, no sensitivity analysis will be carried out for the transcriptomics endpoints.

Please see the separate document **“Statistical Analysis Plan”** for additional information.

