6.3.2. The Intent-to-Treat (ITT) Analysis Population

The ITT population includes all subjects who received at least one study vaccination and contributed both pre- and at least one post-study vaccination blood samples for immunogenicity testing for which valid results were reported. Subjects will be analyzed according to the study group to which they were randomized.

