6.5. Missing Data

Unless otherwise specified, missing data will be maintained as missing for all analyses and no imputation will be performed for missing values.

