8. IMMUNOLOGY EVALUATION

8.1. Antibody Analyses

The primary immunogenicity antibody endpoint analysis will be based on anti-EBOV GP ELISA titer. Exploratory endpoint analysis will assess anti-EBOV neutralizing antibody titers (anti-EBOV GP NEUT50 and anti-EBOV GP NEUT40). All antibody analyses will be conducted for both the ITT and PP analysis populations. Subject level antibody data for anti-EBOV GP ELISA and anti-EBOV GP NEUT will be presented as shown in [Listing 9](#).

For each study arm and analysis population, titers for each study visit will be summarized by tabulating the number of observations, geometric mean and 95% CI of the geometric mean (based on Student's t-distribution) ([Table 18](#)). Per-visit geometric mean titers and 95% CIs will be visualized across study visits by study arm using time trend plots as presented in [Figure 2](#). Similarly, the geometric mean fold rise relative to pre-vaccination (Day 1) will be summarized ([Table 19](#) and [Figure 2](#)). For each study arm and analysis population, the number of subjects that achieved seroconversion for each post-first vaccination study visit will be summarized by tabulating numbers, percentages, and associated 95% CIs (based on Clopper-Pearson) ([Table 20](#)). Per-visit seroconversion percentages and 95% CIs will be visualized across post-first vaccination study visits by study arm using time trend plots as presented in [Figure 3](#). For the exploratory assessment of neutralization titers (anti-EBOV GP NEUT50 and anti-EBOV GP NEUT40), GMTs and GMFRs will be tabulated and visualized as presented in [Table 18](#), [Table 19](#), and [Figure 2](#).

Significant differences in anti-EBOV GP ELISA and anti-EBOV neutralizing antibody titers (anti-EBOV GP NEUT50 and anti-EBOV GP NEUT40) between study groups for each post-second vaccination time points will be evaluated using a two-sided Welch's t-test using an individual alpha of 0.05 ([Table 21](#)). Differences in anti-EBOV GP ELISA-based seroconversion at post-second vaccination time points will be assessed using a two-sided Fisher's exact test using an individual alpha of 0.05 ([Table 22](#)).

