14.2 Immunogenicity Data

Table 18: Anti-EBOV GP ELISA Geometric Mean Titer (GMT) Results with 95% Confidence Intervals by Study Day and Treatment Group - Intent-to-Treat Population

Study Visit Day	Treatment Group	n	GMT	95% CI [†]
Day 1 First Vaccination	Study Arms 1, 2, and 3 (ChAd3) (N=X)*	n	x.x	x.x – x.x
Day 8 Post-First Vaccination (Second Vaccination)	Study Arms 1, 2, and 3 (ChAd3) (N=X)*	n	x.x	x.x – x.x
Day 8 Post-Second Vaccination	Study Arm 1(ChAd3+Placebo) (N=X)	n	x.x	x.x – x.x
	Study Arm 2 (ChAd3+ChAd3) (N=X)	n	x.x	x.x – x.x
	Study Arm 3 (ChAd3+MVA-BN) (N=X)	n	x.x	x.x – x.x
Day 15 Post-Second Vaccination	Study Arm 1 (ChAd3+Placebo) (N=X)	n	x.x	x.x – x.x
	Study Arm 2 (ChAd3+ChAd3) (N=X)	n	x.x	x.x – x.x
	Study Arm 3 (ChAd3+MVA-BN) (N=X)	n	x.x	x.x – x.x
Day 22 Post-Second Vaccination	Study Arm 1 (ChAd3+Placebo) (N=X)	n	x.x	x.x – x.x
	Study Arm 2 (ChAd3+ChAd3) (N=X)	n	x.x	x.x – x.x
	Study Arm 3 (ChAd3+MVA-BN) (N=X)	n	x.x	x.x – x.x
Day 29 Post-Second Vaccination	Study Arm 1 (ChAd3+Placebo) (N=X)	n	x.x	x.x – x.x
	Study Arm 2 (ChAd3+ChAd3) (N=X)	n	x.x	x.x – x.x
	Study Arm 3 (ChAd3+MVA-BN) (N=X)	s	x.x	x.x – x.x

N=Number of subjects in the Intent-to-Treat Population. n = Number of subjects with valid test results.

*: Subjects in treatment groups that received the same study product were analyzed jointly.

†: Confidence interval for the geometric mean based on Student's t-distribution.

GMT: Geometric Mean.

Repeat this table to summarize secondary anti-EBOV GP ELISA GMT for the per-protocol population, the exploratory anti-EBOV GP NEUT50 and anti-EBOV GP NEUT40 GMT for the intent-to-treat population, and the exploratory anti-EBOV GP NEUT50 and anti-EBOV GP NEUT40 GMT for the per-protocol population.

Table 19: Anti-EBOV GP ELISA Geometric Mean Fold Rise (GMFR) Results with 95% Confidence Intervals by Study Day and Treatment Group - Intent-to-Treat Population

Study Visit Day	Treatment Group	n	GMFR	95% CI [†]
Day 8 Post-First Vaccination (Second Vaccination)	Study Arms 1, 2, and 3 (ChAd3) (N=X)*	n	x.x	x.x – x.x
Day 8 Post-Second Vaccination	Study Arm 1(ChAd3+Placebo) (N=X)	n	x.x	x.x – x.x
	Study Arm 2 (ChAd3+ChAd3) (N=X)	n	x.x	x.x – x.x
	Study Arm 3 (ChAd3+MVA-BN) (N=X)	n	x.x	x.x – x.x
Day 15 Post-Second Vaccination	Study Arm 1 (ChAd3+Placebo) (N=X)	n	x.x	x.x – x.x
	Study Arm 2 (ChAd3+ChAd3) (N=X)	n	x.x	x.x – x.x
	Study Arm 3 (ChAd3+MVA-BN) (N=X)	n	x.x	x.x – x.x
Day 22 Post-Second Vaccination	Study Arm 1 (ChAd3+Placebo) (N=X)	n	x.x	x.x – x.x

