	Study Arm 2 (ChAd3+ChAd3) (N=X)	n	x.x	x.x – x.x
	Study Arm 3 (ChAd3+MVA-BN) (N=X)	n	x.x	x.x – x.x
Day 29 Post-Second Vaccination	Study Arm 1 (ChAd3+Placebo) (N=X)	n	x.x	x.x – x.x
	Study Arm 2 (ChAd3+ChAd3) (N=X)	n	x.x	x.x – x.x
	Study Arm 3 (ChAd3+MVA-BN) (N=X)	s	x.x	x.x – x.x

N=Number of subjects in the Intent-to-Treat Population. n = Number of subjects with valid test results.

*: Subjects in treatment groups that received the same study product were analyzed jointly.

†: Confidence interval for the geometric mean based on Student's t-distribution.

GMFR represents the geometric mean fold rise in antibody compared to pre-dose 1.

Repeat this table to summarize secondary anti-EBOV GP ELISA GMFR for the per-protocol population, the exploratory anti-EBOV GP NEUT50 and anti-EBOV GP NEUT40 GMFR for the intent-to-treat population, and the exploratory anti-EBOV GP NEUT50 and anti-EBOV GP NEUT40 GMFR for the per-protocol population.

Table 20: Anti-EBOV GP ELISA Seroconversion Results with 95% Confidence Intervals by Study Day and Treatment Group - Intent-to-Treat Population

Study Visit Day	Treatment Group	n	Seroconversion n/N(%)	Seroconversion 95% CI [†]
Day 8 Post-First Vaccination (Second Vaccination)	Study Arms 1, 2, and 3 (ChAd3) (N=X)*	n	x.x	x.x – x.x
Day 8 Post-Second Vaccination	Study Arm 1 (ChAd3+Placebo) (N=X)	n	x.x	x.x – x.x
	Study Arm 2 (ChAd3+ChAd3) (N=X)	n	x.x	x.x – x.x
	Study Arm 3 (ChAd3+MVA-BN) (N=X)	n	x.x	x.x – x.x
Day 15 Post-Second Vaccination	Study Arm 1 (ChAd3+Placebo) (N=X)	n	x.x	x.x – x.x
	Study Arm 2 (ChAd3+ChAd3) (N=X)	n	x.x	x.x – x.x
	Study Arm 3 (ChAd3+MVA-BN) (N=X)	n	x.x	x.x – x.x
Day 22 Post-Second Vaccination	Study Arm 1 (ChAd3+Placebo) (N=X)	n	x.x	x.x – x.x
	Study Arm 2 (ChAd3+ChAd3) (N=X)	n	x.x	x.x – x.x
	Study Arm 3 (ChAd3+MVA-BN) (N=X)	n	x.x	x.x – x.x
Day 29 Post-Second Vaccination	Study Arm 1 (ChAd3+Placebo) (N=X)	n	x.x	x.x – x.x
	Study Arm 2 (ChAd3+ChAd3) (N=X)	n	x.x	x.x – x.x
	Study Arm 3 (ChAd3+MVA-BN) (N=X)	s	x.x	x.x – x.x

N=Number of subjects in the Intent-to-Treat Population. n = Number of subjects with valid laboratory results.

*: Subjects in treatment groups that received the same study product were analyzed jointly.

†: Confidence interval for seroconversion is based on Based on Clopper-Pearson.

Seroconversion is defined as having a pre-dose titer ≤ 50 and post-dose titer of > 50 or fold rise ≥ 4 as compared to baseline titer > 50 .

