Repeat this table to compare anti-EBOV GP ELISA GMT for the per-protocol population, the exploratory anti-EBOV GP NEUT50 and anti-EBOV GP NEUT40 GMT for the intent-to-treat population, and the exploratory anti-EBOV GP NEUT50 and anti-EBOV GP NEUT40 GMT for the per-protocol population.

Table 22: Comparison of Anti-EBOV GP ELISA Seroconversion Between Treatment Groups Post-Second Vaccination by Study Day and Treatment Group - Intent-to-Treat Analysis Population

Study Visit Day	Group A	Group B	n/N (%) A	n/N (%) B	Odds Ratio (95% CI)	P-Value [†]
Day 8 Post-Second Vaccination	Study Arm 1 (ChAd3+Placebo) (N=X)	Study Arm 2 (ChAd3+ChAd3) (N=X)	xx/xx (xx.x%)	xx/xx (xx.x%)	x.xx (x.xx - x.xx)	0.xxx
	Study Arm 1 (ChAd3+Placebo) (N=X)	Study Arm 3 (ChAd3+MVA-BN) (N=X)	xx/xx (xx.x%)	xx/xx (xx.x%)	x.xx (x.xx - x.xx)	0.xxx
	Study Arm 2 (ChAd3+ChAd3) (N=X)	Study Arm 3 (ChAd3+MVA-BN) (N=X)	xx/xx (xx.x%)	xx/xx (xx.x%)	x.xx (x.xx - x.xx)	0.xxx
Day 15 Post-Second Vaccination	Study Arm 1 (ChAd3+Placebo) (N=X)	Study Arm 2 (ChAd3+ChAd3) (N=X)	xx/xx (xx.x%)	xx/xx (xx.x%)	x.xx (x.xx - x.xx)	0.xxx
	Study Arm 1 (ChAd3+Placebo) (N=X)	Study Arm 3 (ChAd3+MVA-BN) (N=X)	xx/xx (xx.x%)	xx/xx (xx.x%)	x.xx (x.xx - x.xx)	0.xxx
	Study Arm 2 (ChAd3+ChAd3) (N=X)	Study Arm 3 (ChAd3+MVA-BN) (N=X)	xx/xx (xx.x%)	xx/xx (xx.x%)	x.xx (x.xx - x.xx)	0.xxx
Day 22 Post-Second Vaccination	Study Arm 1 (ChAd3+Placebo) (N=X)	Study Arm 2 (ChAd3+ChAd3) (N=X)	xx/xx (xx.x%)	xx/xx (xx.x%)	x.xx (x.xx - x.xx)	0.xxx
	Study Arm 1 (ChAd3+Placebo) (N=X)	Study Arm 3 (ChAd3+MVA-BN) (N=X)	xx/xx (xx.x%)	xx/xx (xx.x%)	x.xx (x.xx - x.xx)	0.xxx
	Study Arm 2 (ChAd3+ChAd3) (N=X)	Study Arm 3 (ChAd3+MVA-BN) (N=X)	xx/xx (xx.x%)	xx/xx (xx.x%)	x.xx (x.xx - x.xx)	0.xxx
Day 29 Post-Second Vaccination	Study Arm 1 (ChAd3+Placebo) (N=X)	Study Arm 2 (ChAd3+ChAd3) (N=X)	xx/xx (xx.x%)	xx/xx (xx.x%)	x.xx (x.xx - x.xx)	0.xxx
	Study Arm 1 (ChAd3+Placebo) (N=X)	Study Arm 3 (ChAd3+MVA-BN) (N=X)	xx/xx (xx.x%)	xx/xx (xx.x%)	x.xx (x.xx - x.xx)	0.xxx
	Study Arm 2 (ChAd3+ChAd3) (N=X)	Study Arm 3 (ChAd3+MVA-BN) (N=X)	xx/xx (xx.x%)	xx/xx (xx.x%)	x.xx (x.xx - x.xx)	0.xxx

N=Number of subjects in the Intent-to-Treat Population.

[†]: Based on Fisher's exact test.

n A: Number of subjects with valid laboratory results for comparison group A.

n B: Number of subjects with valid laboratory results for comparison group B.

Repeat this table to compare anti-EBOV GP ELISA seroconversion for the per-protocol population.

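### Seroconversion percentages are set on the whole analysis population, so a subject with no result at a visit is counted as not seroconverted; the Table 20 and 22 footnotes also mislabel the numerator

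*SAP*

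**What the plan says.** SAP 6.1 gives one rule for every categorical variable: "The frequency and percentages (based on the analysis population size) of observed levels will be reported for all categorical measures". For continuous variables the same section uses the non-missing sample size.

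SAP 8.1 describes the seroconversion summary: "the number of subjects that achieved seroconversion for each post-first vaccination study visit will be summarized by tabulating numbers, percentages, and associated 95% CIs". It names Clopper-Pearson for the interval and a two-sided Fisher's exact test between arms, but no denominator.

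Table 20 shows seroconversion as n/N (%), with the footnote "N=Number of subjects in the Intent-to-Treat Population. n = Number of subjects with valid laboratory results". Table 22 also shows n/N (%) per arm, defines N as the ITT population, and adds "n A: Number of subjects with valid laboratory results for comparison group A", with the same wording for group B. The GMT and GMFR shells (Tables 18 and 19) carry the footnote "n = Number of subjects with valid test results".

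Under SAP 6.3.2, ITT subjects are vaccinated subjects who "contributed both pre- and at least one post-study vaccination blood samples for immunogenicity testing for which valid results were reported". On missing data, SAP 6.5 says: "Unless otherwise specified, missing data will be maintained as missing for all analyses and no imputation will be performed for missing values". Protocol 11.4.5 says: "As missing data are expected to be minimal, no imputation will be performed for missing values".

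For the per-protocol (PP) repeats, SAP 6.3.3, Table 13 and Listing 5 remove data visit by visit. The Table 12 footnote counts a subject as excluded from PP only when every visit is excluded.

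**The concern.** Seroconversion is a named secondary endpoint in a trial sized for estimation, so the percentage and its interval are the result. Dividing by the whole population treats an absent assay result as a failure to respond. That is a form of imputation, always in the downward direction, in a plan that says it does not impute. The GMT, GMFR and seroconversion rows for the same arm and visit would then rest on different sets of subjects.

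The footnotes compound this. They leave no symbol for the number who seroconverted, so the shell does not match SAP 8.1.

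**Working it through.** **What the text implies for a missing result.**
1. SAP 6.1 and the N footnotes set the denominator at N, the ITT population.
2. ITT entry needs a baseline result and any one later result, so a subject can be in ITT with nothing at, say, Day 22.
3. That subject cannot meet the seroconversion definition at Day 22 but stays in N. The subject therefore adds to the non-seroconverted count in the percentage, the interval and the Fisher 2x2 table.
4. In the PP repeats, a subject whose visit was excluded as out of window can remain in PP under the Table 12 footnote, and so could remain in that visit's denominator. SAP 6.1 also says arm labels carry the population size relevant to the analysis, so this is a possibility and not a stated rule.

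**Inputs for the size.** N = 20 per arm (Protocol Table 1, SAP Table 1). The documents give no missing rate; I assume m = 1 to 2 of 20. They give no expected seroconversion rate for this trial; I assume 70 to 100% at the later visits, from the 70%, 90% and 100% antibody-response figures that Protocol 2.2 cites from other trials at about one month. There is no planned figure to reproduce, because the tables are empty shells.

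**Formula.** With x seroconverters among n = N − m tested and r = x/n, the gap is x/n − x/N = r × m/N. For m = 1 and N = 20 this is 0.70/20 = 3.5 points, 0.90/20 = 4.5 points and 1.00/20 = 5.0 points.

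**Rates with Clopper-Pearson 95% intervals.**

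| Missing | Seroconverters | Denominator N = 20 | Denominator = valid results |
|---|---|---|---|
| 1 | 19 | 95.0% (75.1–99.9) | 19/19 = 100% (82.4–100) |
| 2 | 18 | 90.0% (68.3–98.8) | 18/18 = 100% (81.5–100) |
| 1 | 17 | 85.0% (62.1–96.8) | 17/19 = 89.5% (66.9–98.7) |
| 1 | 13 | 65.0% (40.8–84.6) | 13/19 = 68.4% (43.4–87.4) |

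With m = 0 the two columns are identical.

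**Fisher test, two-sided.**
- 14/20 in one arm, 19 seroconverters with 1 missing in the other: p = 0.091 against 19/20 and p = 0.020 against 19/19.
- 20/20 in one arm, 15 seroconverters with 2 missing in the other: p = 0.047 against 15/20 and p = 0.097 against 15/18.

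One or two missing results can therefore move p across 0.05 in either direction.

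**Numerator label.** Read literally, n/N with n as valid results would print 18/20 = 90.0% whenever 18 results are valid, whatever the response. SAP 8.1 shows that this is not the intent.

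**The case against.** The strongest reply is that the denominator is written down. SAP 6.1 and both N footnotes agree on population size. SAP 6.5 opens with an exception clause that 6.1 may satisfy. Tables 18 and 19 are continuous summaries with their own rule, so they support a valid-result basis only by analogy. Counting missing as non-response is a legitimate conservative convention. All of this stands as a reading of the text. A reader might infer that the documents are evenly split on the denominator; they are not, and the literal wording leans to population size. What remains is that the SAP never says a missing result counts as non-response, and never reconciles that consequence with its no-imputation rule.

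A reader might also infer that the tables would report assay completeness in place of seroconversion. SAP 8.1 and the Table 20 column heading rule that out. In Table 22 the footnote defines n A and n B, which are columns of Table 21 and not of Table 22, so it was probably carried over.

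Nor are valid-result counts lost: Table 20 has an n column and Table 21 prints counts by arm for the same assay, visit and population. The Fisher tests are exploratory and unadjusted, no formal null hypothesis is tested, and Protocol 11.4.5 expects few missing data. These points limit the severity but do not remove the bias in the estimate.

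**Conclusion.** The point holds as a minor one. The plan's stated rule biases a secondary-endpoint rate and its interval downward whenever an ITT subject lacks a result at a visit. Under the assumed 1 to 2 missing of 20 and 70 to 100% conversion, the cost is about 3.5 to 5 points per missing result.

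Two further inferences should be avoided. First, the assumed range should not be applied to the pooled Day 8 row: the cited rates were measured about a month after vaccination, and nothing in the documents supports them one week after the prime. Second, it would be wrong to conclude that the choice cannot affect significance. If every tested subject converts, 20/20 against 20 − m of 20 reaches p < 0.05 only at m = 5 (p = 0.047). That is a special case, and the examples above cross 0.05 in both directions with one or two missing.

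The numerator issue is a labelling error. The PP denominator is unclear, not demonstrably wrong.

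**What to change.** In SAP 6.1 and 8.1, exempt seroconversion from the population-size rule. There and in the footnotes of Tables 20 and 22, define:
- the numerator as subjects meeting the seroconversion definition at that visit;
- the denominator, for the percentage, the Clopper-Pearson interval and the Fisher test alike, as subjects in the analysis population with valid Day 1 and visit results who are not excluded at that visit.

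Give the numerator its own symbol and keep n for valid results. Extra valid-count columns in Table 22 are optional, since Tables 20 and 21 already print them.

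Separately, align the fold-rise threshold: Protocol 11.4.3 requires more than 4-fold, while Protocol 3.2.2 and SAP 3.3 accept 4-fold or more. An exact 4-fold rise from a baseline titer above 50 is classified differently under the two.

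The cost is SAP and footnote wording. The one downside is that denominators will differ slightly from visit to visit.
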